1. INTRODUCTION

1.1 Background and rationale for conducting this study

Roxadustat is an orally administered investigational novel drug in development for the treatment of anemia associated with chronic kidney disease (CKD), including end-stage renal disease (ESRD). It is currently in global Phase 3 clinical development and has not been marketed in any country. Roxadustat is a potent and reversible orally active hypoxia-inducible factor prolyl hydroxylase inhibitor (HIF-PHI) that transiently induces hypoxia-inducible factor (HIF) stabilization and leads to a functional HIF transcriptional response that mimics the erythropoietic response associated with exposure of humans to intermittent hypoxia (Semenza 1998). HIF induces expression not only of erythropoietin, but also the erythropoietin receptor and proteins that promote iron reabsorption and recycling (Peyssonaux et al 2008). Thus, roxadustat pharmacologically stimulates erythropoiesis via the HIF pathway and in a manner consistent with the body's normal homeostatic response to hypoxia, but under normoxic conditions. Potential advantages of roxadustat compared with erythropoietin analogues for treatment of anemia in patients with CKD treated with dialysis include oral administration, greater cardiovascular (CV) safety and reduced need for intravenous (IV) iron therapy. The clinical data collected thus far suggest that roxadustat is generally safe and well tolerated in healthy adult patients, and in dialysis and non-dialysis CKD patients with anemia treated up to 60 weeks. Information from the clinical studies conducted with roxadustat can be found in the Investigator's Brochure.

The objective of the current study is to assess the efficacy, safety and tolerability, with the primary focus on Hemoglobin efficacy and CV safety of roxadustat in patients with ESRD treated by dialysis (hemodialysis [HD] or peritoneal dialysis [PD]).

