5. Proportion of total time of interpolated Hb values within the interval 10-12 g/dL from week 28 until week 52 will be estimated for each subject and used as dependent variable. The difference between roxadustat and epoetin alfa will be compared using ANCOVA. Baseline Hb will be used as a covariate and the treatment groups, CV history, geographic region and dialysis duration as fixed effects. Non-inferiority between the groups will be declared, and this test as successful, if the lower bound of

the 2-sided 95% confidence interval of the difference between roxadustat and epoetin alfa exceeds -0.15.

6. The average monthly IV iron use during Week 36 to EOS will be compared between the two treatment groups using a Wilcoxon Rank Sum test. Superiority will be declared if the p-value is less than 0.05.
7. Time-to-first (and proportion of subjects receiving) RBC transfusion as rescue therapy. The baseline Hb, geographic region, dialysis duration and CV history will be included as covariates.

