4.2.2 Confirmatory analysis for the efficacy endpoints

To address the issue of multiple testing while maintaining the overall type-I error, adopting a 5% two-sided significance level, a closed testing sequence will be used for the efficacy endpoints. First, the primary efficacy endpoint analysis according to Section 0 will be performed. If successful, the testing will continue with the secondary efficacy endpoints in the order as specified in Section 4.3.4. Confirmatory statistical hypothesis testing will continue until the first statistically non-significant treatment difference is observed. However, treatment comparisons following and including the first non-significant comparison will be examined in an exploratory manner.

All analyses other than part of this confirmatory analysis will be interpreted descriptively. Consequently, no adjustments for multiplicity will be necessary for such analyses. Ninety-five percent confidence intervals will be calculated, where appropriate, as measures of study precision. P-values may be calculated but are to be regarded as descriptive.

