4.3.4 Secondary efficacy endpoints analyses

Secondary efficacy endpoints will be tested using a fixed sequence approach to adjust for multiple testing. If the p-value from a test is less than 0.05, the test will be declared as successful and the analysis will continue to the next comparison in the sequence. Formal statistical hypothesis testing will be stopped as soon as a test is accompanied by a p-value ≥ 0.05 . The PPS will be used for the first secondary endpoint for non-inferiority, OT+3 analysis set will be used for the secondary endpoints related to RBC transfusion as rescue therapy, and the ITT analysis data set will be used for all the remaining secondary endpoints.

1. The EU primary endpoint for non-inferiority is the first secondary efficacy endpoint for FDA (see above).

2. Mean change from baseline in LDL cholesterol to week 24 will be analysed using ANCOVA. Baseline Hb and baseline LDL will be used as covariates and treatment groups, CV history, geographic region and dialysis duration as fixed effects. Superiority will be declared if the upper bound of the 2-sided 95% confidence interval of the difference between roxadustat and epoetin alfa falls below 0.
3. Mean change in Hb from baseline to the subjects mean level from week 28 to week 52 in subjects with baseline hsCRP greater than the Upper Limit Normal (ULN) will be analysed analogously as the primary efficacy endpoint. Superiority of roxadustat compared to epoetin alfa will be declared, and this test as successful, if the lower bound of the 2-sided 95% confidence interval of the difference between roxadustat and epoetin alfa exceeds 0 g/dL.
4. Proportion of total time of interpolated Hb values ≥ 10 g/dL from week 28 until week 52 will be estimated for each subject and used as dependent variable. The difference between roxadustat and epoetin alfa will be compared using ANCOVA. Baseline Hb will be used as a covariate and the treatment groups, CV history, geographic region and dialysis duration as fixed effects. Non-inferiority between the groups will be declared, and this test as successful, if the lower bound of the 2-sided 95% confidence interval of the difference between roxadustat and epoetin alfa exceeds -0.15.

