5. Proportion of total time of interpolated Hb values within the interval 10-12 g/dL from week 28 until week 52 will be estimated for each subject and used as dependent variable. The difference between roxadustat and epoetin alfa will be compared using ANCOVA. Baseline Hb will be used as a covariate and the treatment groups, CV history, geographic region and dialysis duration as fixed effects. Non-inferiority between the groups will be declared, and this test as successful, if the lower bound of the 2-sided 95% confidence interval of the difference between roxadustat and epoetin alfa exceeds -0.15.
6. The average monthly IV iron use during Week 36 to EOS will be compared between the two treatment groups using a Wilcoxon Rank Sum test. Superiority will be declared if the p-value is less than 0.05.
7. Time-to-first (and proportion of subjects who received) RBC transfusion as rescue therapy, will be analysed using Cox proportional hazard model. The baseline Hb, geographic region, dialysis duration and CV history will be included as covariates. Non-inferiority will be claimed, and this test successful, if the upper bound of the 2-sided 95% CI for the hazard ratio (roxadustat/epoetin alfa) is less than or equal to 1.8.

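### The IV iron step declares superiority on a two-sided p-value without a direction, and its rank test ignores the country strata used for randomisation (minor)

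*SAP*

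**What the plan says.** The IV iron comparison is item 6 of seven in the fixed sequence (SAP 4.3.4, Protocol 8.6.5). For average monthly use from week 36 to end of study, the SAP's decision rule is "Superiority will be declared if the p-value is less than 0.05". The protocol has the same test and rule: use "will be compared between the two treatment groups using a Wilcoxon Rank Sum test. Superiority will be declared if the p-value is less than 0.05". The item names no favoured arm, no sign and no estimate. The ITT set applies.

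Two general rules surround it:
- **Level.** SAP 4.2.2 states that, "adopting a 5% two-sided significance level, a closed testing sequence will be used for the efficacy endpoints". It continues testing until the first non-significant difference and mentions no direction.
- **Gate.** SAP 4.3.4 says "If the p-value from a test is less than 0.05, the test will be declared as successful", after which testing moves on. Protocol 8.6.5 has the same rule.

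The two other superiority steps do state a direction in the SAP. For LDL (item 2) the upper bound of the "confidence interval of the difference between roxadustat and epoetin alfa falls below 0"; for Hb in inflamed subjects (item 3) the lower bound must exceed 0. Step 7 (RBC transfusion) requires in the SAP that the "upper bound of the 2-sided 95% CI for the hazard ratio (roxadustat/epoetin alfa) is less than or equal to 1.8"; Protocol 8.6.5 gives no limit for that step.

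The IV iron objective in SAP 1.1.3 is a neutral comparison. The intended direction appears only in Protocol 1.1, which lists "reduced need for intravenous (IV) iron therapy" among the potential advantages of roxadustat.

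On design, Protocol 3.5 and 7.2.1 block and stratify randomisation by country. The rank test in item 6 uses no strata.

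**The concern.** A confirmatory rule should not be able to pass on an unfavourable result. A two-sided rank test with p below 0.05 says that the arms differ, not which arm used less iron. Most other steps get their direction from a named confidence bound. A rank test supplies no such bound by default, so item 6 needs its direction in words.

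At stake are a wrong label on one secondary endpoint and the opening of the last step in the sequence after an adverse result.

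The second matter is efficiency. When subjects are randomised in blocks within country, differences in iron practice between countries are largely balanced across the arms. An unstratified rank test still counts that variation as noise, so it rejects less often than its nominal level when use differs between countries.

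**Working it through.** **Plan's own figure.** The documents give no power or assumed effect for IV iron. Their only stated power concerns the primary Hb endpoint and reproduces: 0.45 / (1.25 × √(2/300)) = 4.409; 4.409 − 1.960 = 2.449; power 0.993, against the stated 99% or more. It has no bearing on item 6.

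**Where the rules leave direction open (SAP)**

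| Step | Direction in the item | Item itself says when the test is successful |
|---|---|---|
| 1, 3, 4, 5, 7 | Yes, a confidence bound and a limit | Yes |
| 2 (LDL) | Yes, upper bound below 0 | No |
| 6 (IV iron) | No | No |

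At step 6 both the label and the gate lack a direction. At step 2 the label has one, but only the general gate sentence defines success.

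**Chance of a wrong-direction pass.** Let θ be the probability that a roxadustat subject uses more IV iron than an epoetin alfa subject, counting half of ties. With n per arm and few ties, SE(θ) = √((2n+1)/(12n²)), and the wrong-direction probability is 1 − Φ(1.96 − (θ − 0.5)/SE). The values of θ and n are assumptions.

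- n = 500: SE = √(1001/3,000,000) = 0.01827.
- n = 1000: SE = √(2001/12,000,000) = 0.01291.
- Example, θ = 0.52 and n = 1000: 0.02/0.01291 = 1.549; 1 − Φ(0.411) = 0.341.

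| θ | Wrong-direction pass, n = 500 | n = 1000 |
|---|---|---|
| 0.45 (lower use on roxadustat) | <0.0001 | <0.0001 |
| 0.50 (equal) | 0.025 | 0.025 |
| 0.51 | 0.079 | 0.118 |
| 0.52 | 0.194 | 0.341 |
| 0.53 | 0.375 | 0.642 |

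Requiring the favourable direction takes the pass rate with equal arms from 0.050 to 0.025. At θ = 0.45 power is unchanged (0.782 and 0.972).

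Simulations with many zero users agree. With 30, 50 or 70% users and 1,400 or 2,000 subjects, equal arms gave a wrong-direction p below 0.05 in 2.2 to 2.7% of trials. With the roxadustat user share 5 points lower, this happened in 0 of 24,000 trials. With 50% non-users on epoetin alfa, 1,000 per arm and 3 points more users on roxadustat, it happened in 24%. All these figures take step 6 as reached; the earlier steps were not simulated jointly.

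**Country.** If a share R of the rank variance lies between countries and blocking balances it fully, the true variance of the statistic is (1 − R) times the variance the test assumes. The real size is then 2(1 − Φ(1.96/√(1 − R))). For an assumed R of 0.2: 1.96/√0.8 = 2.191, size 2.8%.

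Simulation used 20 or 30 countries of unequal size, blocks of 4, 50% base use, a log-odds effect of 0 or −0.25, 2,000 replicates per cell, and countries under 20 subjects pooled into four regions:

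| Between-country SD (logit) | Size, unstratified | Power gain, van Elteren |
|---|---|---|
| 0.5 | 4.2–5.1% | 0.1–0.5 points |
| 1.0 | 2.8–4.5% | 2.8–3.5 points |
| 1.5 | 2.3–3.4% | 4.9–6.1 points |

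Van Elteren size was 4.3 to 6.0%; the simulation error is about 0.5 points (√(0.05 × 0.95/2000) = 0.0049). A second simulation (20 countries, 1,400 subjects) gave 3.0 to 3.8% unstratified, 4.6 to 6.0% for van Elteren, and a gain of about 1 to 5 points.

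**The case against.** The strongest reply is that ordinary reading settles the matter. Item 6 does not say superiority of roxadustat, so a significant result with higher use on roxadustat would simply show that epoetin alfa did better. The background gives the intended benefit, and SAP 4.3.5.5 reports IV iron use by arm, so a reversal could not go unnoticed. A reversal is also unlikely: Protocol 7.7.3 sets conditions for starting IV iron on roxadustat, while the epoetin alfa arm follows standard of care. All of this stands, and it is why the point is minor. It does not repair the gate, which opens on p below 0.05 whatever the sign. Nor is direction safe to leave to inference: for LDL, Protocol 8.6.5 has the upper bound exceeding 0 where the SAP has it falling below 0.

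Three stronger readings are tempting, and the documents do not support them:
- **That a direction added to the superiority sentence is enough.** The gate is a separate sentence, so a wrong-direction result would lose the label but still open step 7.
- **That item 6 stands alone.** Item 2 also leaves success to the general gate, with five later steps behind it rather than one. Item 6 differs in that its label lacks a direction too.
- **That the familywise error is inflated.** The test keeps its two-sided 5% level and step 7 keeps its own limit. What is uncontrolled is the directional claim.

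On country, one may reply that the plan's adjustment variables (SAP 1.2.3) include US vs Ex-US region but not country, that the Wilcoxon test is valid, and that the gain rests on assumed variation. Each is true. The van Elteren size of up to 6.0% is about two simulation errors above nominal, so better calibration is not proven at every setting. Analysis by the randomised strata remains reasonable, but it is an improvement and not the correction of an error.

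**Conclusion.** The point holds as a minor drafting fault in item 6 of both documents. Taken literally, label and gate together let significantly higher IV iron use on roxadustat count as superiority and open step 7. The practical risk is small: 2.5% with equal arms, effectively zero if roxadustat lowers use, and material only if use is truly higher on roxadustat (0.19 to 0.34 at θ = 0.52 with 500 to 1,000 per arm). Step 7 must still meet its 1.8 limit, although only the SAP states it. The wording gap is certain from the text; the probabilities rest on assumed effects, user shares and numbers analysed.

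The exploratory IV iron comparisons need no change, because for analyses outside the confirmatory sequence SAP 4.2.2 says "P-values may be calculated but are to be regarded as descriptive".

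The unstratified test is valid but conservative when iron use differs between countries. Stratifying would gain about 0 to 6 points of power for an assumed between-country SD of 0.5 to 1.5 on the logit scale.

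**What to change.** **(a) Direction and success, both documents.** Replace the decision sentence of item 6 with: *Superiority will be declared, and this test successful, only if the two-sided p-value is less than 0.05 and the rank statistic shows lower average monthly IV iron use on roxadustat.* Direction is tied to the rank statistic because both medians could be zero. Add the same success wording to item 2; in the protocol the direction of its LDL bound must be reconciled with the SAP at the same time. If only the SAP is changed, its Section 6 statement that nothing departs from protocol version 8.0 must be updated. The cost is one sentence per item and no loss of power.

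**(b) Country.** Use a van Elteren test stratified by country. Pool small countries within the four regions of SAP 4.3.7 by a rule fixed before database lock, for example countries with fewer than 20 analysed subjects (an assumed threshold). The test is still rank-based, so it keeps the reason given in SAP 6.1 for choosing a rank test. If the main test can no longer be changed, report this as a sensitivity analysis. The cost is one test option and one pooling sentence; the small downside is having to settle the pooling rule in advance.

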4.3.5 Exploratory endpoint analysis

The baseline value for each exploratory variable is defined as the last measurement of the variable prior to randomization, including the measurement from the randomization visit, unless stated otherwise.

The analysis set to be used for all exploratory analyses will be ITT analysis set, unless specified otherwise. The variables will be analysed as follows:

4.3.5.1 Hb related exploratory endpoint analysis

- Mean change from baseline in Hb to the subjects mean level from week 28 to EOT will be analyzed using multiple imputation with ANCOVA as described in Section 4.2.6. The mean change from baseline will only be imputed for subjects with no measurements from week 28 to EOT. Non-inferiority of roxadustat compared to epoetin alfa will be declared, and this test as successful, if the lower bound of the 2-sided 95% confidence interval of the difference between roxadustat and epoetin alfa exceeds -0.75 g/dL.
- Mean change in Hb from baseline to the subjects mean level from week 28 to week 36 in subjects with baseline hsCRP greater than the Upper Limit Normal (ULN) will be analysed analogously as the primary efficacy endpoint. PPS will be used.
- Proportion of total time of interpolated Hb values ≥ 10 g/dL from week 28 until week 36 will be estimated for each subject and used as dependent variable. The difference between roxadustat and epoetin alfa will be compared using ANCOVA with treatment group, geographic region and CV history as fixed factors and baseline Hb and baseline eGFR as covariates. PPS will be used.
- Time to achieving target Hb for anemic (Hb < 10 g/dL at baseline) subjects who were ESA-naïve or near ESA-naïve (no ESA use ≤ 4 weeks prior to randomization). This will be analyzed analogously as Time to first rescue therapy (composite). Target Hb is achieved when Hb level is within 10-12 g/dL at two consecutive measurements.
- Estimation of median time (in weeks) to achieve target Hb for anemic (Hb < 10 g/dL who were ESA-naïve or near ESA-naïve (no ESA use ≤ 4 weeks prior to randomization), based on the definition of two consecutive Hb levels within 10-12 g/dl, by treatment arm.
- Proportion of ESA-naïve anemic patients achieved Hb response by Week 24 in the subset of patients who were anemic (Hb < 10 g/dL at baseline) and were ESA-naïve or near ESA-naïve (no ESA use ≤ 4 weeks prior to randomization).

Hb response (Yes/No), where Yes is defined as:

- Hb ≥ 11.0 g/dL and Hb increase from baseline by ≥ 1.0 g/dL, for subjects with baseline Hb > 8.0 g/dL; or
- Hb increase from baseline by ≥ 2.0 g/dL, for subjects with baseline Hb ≤ 8.0 g/dL

at two consecutive visits [dates] (with available data) separated at least 5 days during the first 24 weeks of treatment without having received rescue therapy

(RBC transfusion, ESA, or IV iron) prior to Hb response. The proportion of responders in the primary efficacy variable will be compared using Miettinen & Nurminen model, adjusting for the region, history of CV, baseline Hb (≤ 8 , > 8 g/dL) and dialysis duration, comparing roxadustat to epoetin alfa.

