1.2.3 Stratification variables

The randomization in this study will be stratified by country. The stratification variables for the other studies in the program will be used in the analyses for this study as covariates, with addition of incident vs stable dialysis. The stratification variables are:

1. Baseline Hb (≤ 10.5 g/dL vs > 10.5 g/dL)
2. cardiovascular/cerebrovascular/thromboembolic medical history (Yes vs. No)
3. geographical region (US vs. Ex-US)
4. incident vs. stable dialysis (dialysis duration ≤ 4 months vs > 4 months from the randomization date)

Baseline Hb will be included in the analyses as a continuous covariate, hence, not as a dichotomous factor, unless specified otherwise. Throughout this document, the variable cardiovascular/cerebrovascular/thromboembolic medical history will be shortened as CV history, and the variable incident vs stable dialysis will be shortened as dialysis duration

CV history at baseline will be defined for subjects with history of any of the following diseases:

- Myocardial infarction
- Percutaneous coronary intervention
- Coronary artery bypass
- Cardiac failure congestive
- Ischaemic stroke
- Haemorrhagic stroke
- Cerebrovascular accident

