4.2.5 Analysis of Covariance (ANCOVA)

When using ANCOVA in analysis of change from baseline for a continuous variable, the mean value of all change from baseline values available within the pre-specified timeframe will be used as the dependent variable. Unless specified otherwise, baseline Hb will be used as a covariate and treatment group, cardiovascular history, geographic region and dialysis duration as fixed effects for all analyses. Any further details will be given case-by-case for each endpoint (see Section 4.3). The least squares mean estimates of change from baseline for each treatment group and their difference, and associated 95% CI will be provided.

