4.3.5.2 Rescue therapy related exploratory endpoint analysis

- Time-to-first instance rescue therapy (composite) of receiving RBC transfusions, or erythropoietin analogue as rescue therapy will be analysed analogously as Time to first RBC transfusion in Section 4.3.4. The OT+3 will be used.
- Number of rescue therapy treatments given; RBC transfusion or erythropoietin analogue per PEY will be reported descriptively, together and separately. The OT+3 will be used.
- Proportion of subjects receiving RBC transfusion during week 28 to week 52 will be analysed using Miettinen & Nurminen model adjusting for the region, history of CV and baseline Hb (≤ 8 , > 8 g/dL) and dialysis duration, comparing roxadustat to epoetin alfa. The OT+3 will be used.

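### SAP 4.3.5.1 adjusts one exploratory haemoglobin analysis for an undefined baseline eGFR and leaves out dialysis duration

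*SAP*

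**What the plan says.** The SAP sets a common covariate list and repeats it. SAP 1.2.3 states that "The stratification variables for the other studies in the program will be used in the analyses for this study as covariates", and adds incident versus stable dialysis for this study. The list is therefore baseline Hb, CV history, region and dialysis duration. SAP 4.2.5 makes this the ANCOVA default: unless otherwise specified, "baseline Hb will be used as a covariate and treatment group, cardiovascular history, geographic region and dialysis duration as fixed effects for all analyses".

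Secondary endpoint 4 (SAP 4.3.4, item 4) is the proportion of time with interpolated Hb at or above 10 g/dL over weeks 28 to 52. Its ANCOVA follows the default: "Baseline Hb will be used as a covariate and the treatment groups, CV history, geographic region and dialysis duration as fixed effects".

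SAP 4.3.5.1 plans an analysis of the same quantity over weeks 28 to 36, in the PPS, again by ANCOVA. Here the model is specified "with treatment group, geographic region and CV history as fixed factors" and with "baseline Hb and baseline eGFR as covariates". Dialysis duration is not in it. SAP Table 4 (section 6.1) describes the new week 28 to 36 variables as repeating secondary endpoints 3, 4 and 6 in a shorter window.

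**The concern.** An analysis intended to repeat a secondary endpoint over a shorter window should use the same model, so that a difference between the two results can be attributed to the window. Here one planned covariate has gone and another, mentioned nowhere else in the SAP, has taken its place.

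The incoming covariate is a poor fit for this trial. All subjects receive haemodialysis or peritoneal dialysis, so serum creatinine partly reflects dialysis clearance, and a creatinine-based eGFR has no clear meaning as a measure of kidney function. The outgoing covariate is the one that SAP 1.2.3 added specifically for this study. The protocol's version history explains that recruitment was later restricted to incident dialysis patients, whom it describes as needing higher ESA doses.

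What is at stake is modest. Whoever programs the analysis must either invent an eGFR derivation or depart from the SAP without a record, and the result is then not comparable in model with secondary endpoint 4.

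**Working it through.** No figure in the plan is in dispute, so the check is a comparison of texts.

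**Step 1: model terms side by side.**

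| Term | Default (SAP 4.2.5) | Secondary endpoint 4 (SAP 4.3.4) | Week 28 to 36 repeat (SAP 4.3.5.1) |
|---|---|---|---|
| Treatment group | yes | yes | yes |
| Baseline Hb | yes | yes | yes |
| CV history | yes | yes | yes |
| Region | yes | yes | yes |
| Dialysis duration | yes | yes | **no** |
| Baseline eGFR | no | no | **yes** |

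The difference is a one-for-one swap. Region, CV history and dialysis duration each have two levels, and eGFR would enter as one slope. Both models therefore have five terms at one degree of freedom each, plus the intercept, giving 1 + 5 = 6 parameters. Restoring the planned term in place of eGFR costs no degrees of freedom.

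**Step 2: the other analyses.** Dialysis duration also appears in the other ANCOVAs whose terms the SAP writes out: the multiple imputation models in 4.2.6, the US primary in 4.3.2, items 2 and 5 of 4.3.4, the heart-rate model in 4.3.5.5 on which several others are based, and the time-in-range analysis in 4.3.6. The week 28 to 36 repeats of secondary endpoints 3 (hsCRP subgroup, 4.3.5.1) and 6 (IV iron, 4.3.5.5) take their method by reference to the primary analysis and the secondary IV iron analysis respectively. Only the repeat of endpoint 4 has its own written model, and only that one departs.

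**Step 3: whether baseline eGFR is defined or collected.**
- Protocol Table 2 lists creatinine, not eGFR.
- The baseline characteristics in SAP 4.2.1 do not include eGFR.
- The SAP abbreviation list does not contain it.
- Neither document gives an equation. SAP 4.3.5 has a baseline rule for exploratory variables that might be borrowed, but that settles only which measurement to use.
- In the protocol, eGFR appears in the abbreviation list and in statin dosing text (section 7.7.1.1 and the version history), never as a study measurement.

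**Step 4: whether dialysis duration is available.** SAP 1.2.3 defines it as at most 4 months versus more than 4 months from the randomisation date. SAP 4.2.1 reports it for all randomised subjects.

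**The case against.** The strongest defence is that the SAP permits departures. The default in 4.2.5 carries an exception for cases specified otherwise and adds that "Any further details will be given case-by-case for each endpoint". The model in 4.3.5.1 could be read as such a specification. That answers a charge of breaking a rule. It does not supply a definition for the covariate or explain why a repeat of endpoint 4 should use a different model.

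A second defence is that exact mirroring was never intended, because 4.3.5.1 uses the PPS and secondary endpoint 4 uses the ITT set. The difference in sets is real. However, SAP 4.3.6 also repeats the Hb-related secondary endpoints in the PPS, so a week 28 to 52 result in the same set will exist. Against that result, the covariate swap is the one unexplained difference besides the window.

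A third is that an uninformative covariate does little harm. In a fully randomised comparison this is right: the treatment contrast would not be biased, and the loss is whatever precision dialysis duration would have given, which the documents do not allow one to estimate. The PPS selects on events after randomisation, such as at least 8 weeks of treatment, so the argument is a little weaker there. No bias is shown.

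A reader might also infer that the model cannot be fitted, or that many subjects would drop out of it. The documents do not support either. Creatinine is a listed laboratory variable, clinical chemistry is scheduled at screening and randomisation, and age, sex and race are recorded. What is missing is a formula, and the number lost for want of data could be close to nil.

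**Conclusion.** The point holds as a minor specification error in one exploratory analysis. Baseline eGFR is undefined, unlisted and of no clear meaning in this population, and its presence coincides with the loss of a covariate that SAP 1.2.3, 4.2.5 and secondary endpoint 4 all include. Carry-over from a non-dialysis plan is a plausible explanation: SAP 3.3 labels the programme CKD-NDD where protocol 8.5 has CKD-DD. That is only an inference, and the point does not depend on it.

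No type I error, primary or secondary conclusion is affected, because SAP 4.2.2 treats everything outside the confirmatory sequence as descriptive. The argument about comparability assumes that Table 4 states the purpose of the analysis correctly. If it does not, the undefined covariate remains.

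A reader might extend the point to SAP 4.3.5.2, where the transfusion proportion over weeks 28 to 52 is analysed "adjusting for the region, history of CV and baseline Hb" with Hb cut at 8 g/dL, while 1.2.3 categorises it at 10.5 g/dL. The documents do not show an error there. The list continues with dialysis duration, so all the planned factors are present. SAP 1.2.3 allows categorical Hb where specified, and the stratified method needs categories. The same cut is used for the Hb response analysis in 4.3.5.1. A claim that a cut at 8 g/dL hardly adjusts for Hb would need a baseline Hb distribution, which neither document gives; inclusion criterion 4 sets upper limits only.

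**What to change.** In SAP 4.3.5.1, in the item on the proportion of time with Hb at or above 10 g/dL over weeks 28 to 36, remove baseline eGFR and add dialysis duration as a fixed effect. The model then has baseline Hb as covariate, and treatment group, CV history, geographic region and dialysis duration as fixed effects, matching secondary endpoint 4.

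If eGFR was intended, the SAP should instead give the equation, the measurement used as baseline and the reason for using it in dialysis patients, and should state why dialysis duration is left out.

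The cost is one wording correction. It needs no new data, no change in sample size and no change to the testing sequence.
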